15.2 Baseline demographics

For each study group and the entire group, the mean, standard deviation, minimum & maximum will be presented for continuous data, and absolute and relative frequency will be provided for categorical data. For baseline demographics, only descriptive statistics will be presented.

15.3 Analysis of efficacy endpoints

(1) Analysis of endpoints of main interest

- ① Number of patients with complete healing# of ulcer within 12 weeks
: Subjects who achieved complete healing and had early completion will be included.
- ② Time to complete healing# of ulcer within 12 weeks
: Time to complete healing is calculated as the number of days from baseline (1d).
(# The definition of complete healing: Epithelial tissue covering 100% of the study ulcer, no abrasion or ulceration, intact dermis and epidermis)
- ③ Pressure ulcer size reduction rate based on a scale at each time point

$$\text{Reduction rate} = \frac{\text{Pressure ulcer size on 1d}^* - \text{Pressure ulcer size at each time point from 8d to End-of-Study}^{**}}{\text{Pressure ulcer size on 1d}} \times 100\%$$

* Using a scale-based pressure ulcer area (cm²) measured prior to the study device application

** Using a scale-based pressure ulcer area (cm²) without re-epithelization*** measured at each time point after the study device application

(**Re-epithelization: New epithelial tissue covering the pressure ulcer, with no exudate, transudate, or avascular tissue)

- ① For subjects achieving complete healing within 12 weeks, present frequency and percentage.
 - ② For the time to 100% complete healing, analyze using the Kaplan-Meier method. Subjects not achieving 100% complete healing within 12 weeks will not be considered for evaluation for end point of main interest.
 - ③ For the pressure ulcer size reduction rate, present the mean and standard deviation.
- For the analysis for efficacy, conduct sub-analyses by use of local antibiotics and glucocorticoids for the pressure ulcer during the study.

(2) Analysis of other endpoints

- ① PUSH reduction rate at each time point

$$\text{Reduction rate} = \frac{\text{PUSH score on 1d} - \text{PUSH score at each time point}}{\text{PUSH score on 1d}} \times 100\%$$

- ② Dressing change frequency during the entire study period
: Calculated as the additional dressing frequency beyond twice weekly
- ③ Number of subjects with early completion due to complete healing during the study
- ④ Incidence of new infections at the pressure ulcer until Week 12 based on the CSSC

$$\text{Infection incidence} = \frac{\text{Number of subjects with at least 1 new infection** until Week 12, after the study device application}}{\text{Total number of subjects}} \times 100\%$$

(** Infection: Presence of 'Purulent exudates' or 2 or more symptoms of the CSSC. However, for subjects with an infection at baseline, it is defined as development of an additional symptom other than those confirmed at baseline or recurrence of baseline-identified symptoms after being completely healed.)

For other endpoints, present the mean and standard deviation for continuous variables ①, and frequency and percentage in case of categorical variables ②, ③, and ④.

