8.2 Exclusion criteria

- 1) Any study ulcer of the NPUAP Stage I, II or IV
- 2) Diabetic ulcer or Venous ulcer (or stasis ulcer)
- 3) Past history of surgical treatment within 1 year or irradiation at the target pressure ulcer within 1 year
- 4) Hypersensitivity reaction to this product or povidone-iodine
- 5) Hyperthyroidism or thyroid disorder requiring drug treatment
- 6) Signs of a current underlying systemic infection (sepsis/bacterial infection/tuberculosis) or cellulitis or osteomyelitis
- 7) Type 1 diabetes
- 8) Current malnutrition
- 9) Heavy smoker: Current smoking level of ≥ 1 pack (20 cigarettes)/day of tobacco
- 10) Drug or alcohol addiction
- 11) Requirement of immunosuppressants during the study or current chemotherapy or radiotherapy
- 12) Application of other investigational product/medical device within 1 month prior to the

investigational device application (1d)

13) Pregnant or breastfeeding women

14) Other renal, hepatic, neurological, immunological disorder that may interfere with the wound healing process, at the discretion of the investigator

9. Target number of subjects and the rationale

The target number of subject enrollment is 20 subjects, with 10 subjects per group.

This study has a purely explorative goal so that no formal sample size calculation will be conducted but it was planned to enroll 10 subjects per group as the minimum sample size to achieve study objectives from a scientific perspective.

- ✓ Medifoam group: 10 subjects
- ✓ Betafoam group: 10 subjects

Even if a subject is withdrawn from the study, the subject will not be replaced.

10. Study method

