Purulent exudates Tan, creamy, yellow, or green, thick fluid that's present on a dry gauze dressing removed from the ulcer 1 hour after the wound was cleaned and dressed indicates purulent exudate.	
Sanguinous exudates Bloody fluid that's present on a dry gauze dressing removed from the ulcer 1 hour after the wound was cleaned and dressed indicates sanguinous exudate.	
Serous exudates Thin, watery fluid that's present on a dry gauze dressing removed from the ulcer 1 hour after the wound was cleaned and dressed indicates serous exudate.	
Delayed healing of the ulcer The patient reporting no change, or increase in the volume or surface area of the ulcer, over the preceding 4 weeks indicates delayed healing. Ask the patient if the ulcer has filled with tissue or is smaller around than it was 4 week ago.	
Discoloration of granulation tissue Granulation tissue that is pale, dusky, or dull in color compared to surrounding, health tissue. Note variations of normal, beefy-red appearance of granulation tissue.	
Friable granulation tissue Bleeding of granulation tissue when gently manipulated with a sterile cotton-tipped applicator indicates friable tissue.	
Pocketing at base of wound The presence of smooth, nongranulating pockets of ulcer tissue surrounded by beefy red granulation tissue indicates pocketing.	
Foul odor The ulcer may have a putrid or distinctively unpleasant smell	
Wound breakdown Small open areas in newly formed epithelia tissue not caused by reinjury or trauma indicate wound breakdown.	

[Reference: Sharon Baranoski, Elizabeth A. Ayello, Wound Care Essentials: Practice Principles]

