## (2) Other endpoints

- ① PUSH reduction rate at each time point

$$\text{Reduction rate} = \frac{\text{PUSH score on 1d} - \text{PUSH score at each time point}}{\text{PUSH score on 1d}} \times 100\%$$

- ② Dressing change frequency during the entire study period

: Calculated as the additional dressing frequency beyond twice daily

- ③ Number of subjects with early completion due to complete healing during the study
- ④ Incidence of new infections at the pressure ulcer until Week 12 based on the CSSC

$$\text{Infection incidence} = \frac{\text{Number of subjects with at least 1 new infection}^{**} \text{ until Week 12, after the study device application}}{\text{Total number of subjects}} \times 100\%$$

(\*\* Infection: Presence of 'Purulent exudates' or 2 or more symptoms of the CSSC. However, for subjects with an infection at baseline, it is defined as development of an additional symptom other than those confirmed at baseline or recurrence of baseline-identified symptoms after being completely healed.)

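### In a subject infected at baseline, drainage that clears from purulent to serous counts as a new infection if serous exudate was not ticked at baseline, while persisting pus does not

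*Protocol*

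**What the plan says.** The endpoint is the fourth of the other endpoints in Protocol Section 15.3: the share of subjects who have one or more new infections between first device application and Week 12. The general definition is "Infection: Presence of 'Purulent exudates' or 2 or more symptoms of the CSSC". Subjects already infected at baseline get a different test: "for subjects with an infection at baseline, it is defined as development of an additional symptom other than those confirmed at baseline". A second route to an event in these subjects is the return of a sign that had cleared: "or recurrence of baseline-identified symptoms after being completely healed". Protocol Section 16.1 repeats this, and SAP Section 7.1, other endpoints, item 4, has the same rule: "it is defined as development of an additional symptom other than those confirmed at baseline".

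The checklist in Protocol Section 12.2.6 has 13 items, each with its own tick-box. Drainage takes up three of them: purulent, sanguinous and serous. The purulent item reads "thick fluid that's present on a dry gauze dressing removed from the ulcer 1 hour after the wound was cleaned and dressed indicates purulent exudate". The serous item has the same form but is for thin, watery drainage: "after the wound was cleaned and dressed indicates serous exudate".

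The checklist is completed at Visit 2 before the device is applied (Section 12.1.2) and at each weekly visit to day 85. Section 12.2.6 permits wound culture when infection is suspected, but the endpoint definition does not use the result.

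SAP Section 8, analysis of other endpoints, assigns Fisher's exact test to this endpoint. The Table 0707 shell shows incidence with a 95% confidence interval and has no p-value column. Protocol Section 16.2 says that no formal test will be done.

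**The concern.** The general definition treats pus as sufficient for infection on its own, but not serous fluid. The rule for subjects infected at baseline drops that distinction: any one item absent from the baseline list is enough. When pus gives way to thin watery drainage, one tick disappears and a different one appears, and the rule looks only at the one that appears. An improvement is then recorded as an infection event, while a subject with unchanged pus has no event.

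The endpoint counts subjects with at least one event, so a single visit with this pattern is enough. Protocol Section 5.1 gives a lower risk of wound infection as an expected property of Betafoam, and this is the endpoint that would describe it. Section 5.1 also says that a further trial will draw on this study's results.

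**Working it through.** The plan states no figure on this point, so there is none to reproduce. The check applies the rule as written and then sets the weight of one subject against the arm size.

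**1. The rule as coded.** Infected at baseline: purulent ticked, or at least 2 of the 13 items ticked. If infected at baseline, a visit is a new infection when any item ticked at that visit was not ticked at baseline. If not infected at baseline, a visit is a new infection when purulent is ticked or at least 2 items are ticked. The recurrence clause plays no part in the patterns below.

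**2. Results for single visits.**

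| Ticked at baseline | Ticked at visit | New infection? |
|---|---|---|
| purulent | serous | yes |
| purulent | purulent | no |
| purulent, foul odor, erythema | serous | yes (3 signs fall to 1) |
| purulent, serous | serous | no |
| none | serous | no |

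Serous fluid alone is not an infection in a subject who was uninfected at baseline, but it is an event in one who has improved. The fourth row shows the condition: the problem arises only if serous was not ticked at baseline.

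**3. Reach of the rule.** There are 2^13 = 8192 tick patterns. The empty pattern and the 12 single non-purulent patterns are not infected, which leaves 8192 − 13 = 8179 infected patterns. Of these, 4084 do not have serous ticked, and each becomes a new infection at a visit with serous only. Purulent is ticked in 2048 of the 4084. These count possible patterns; they say nothing about how often they occur.

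**4. Weight of one subject.** The planned arm size is 10 (Protocol Section 9), so one subject not otherwise counted adds 1/10 = 10 percentage points. Exact (Clopper-Pearson) 95% limits are 0 to 30.8% for 0/10 and 0.3 to 44.5% for 1/10. Fisher's exact p against 0/10 in the other arm is 1.00 for 1/10, 0.47 for 2/10, 0.21 for 3/10 and 0.09 for 4/10.

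**5. Effect on the comparison, under assumptions.** Let f be the fraction of an arm with purulent but not serous exudate at baseline, c the probability that it clears to serous, and t the true new-infection risk, with clearing and true infection independent. The reported rate is f[1 − (1 − t)(1 − c)] + (1 − f)t. None of f, c or t is in the documents. Assume t = 5% for Betafoam and 15% for Medifoam, a true difference of 10 points.

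| c, Betafoam / Medifoam | f | Betafoam | Medifoam |
|---|---|---|---|
| 55% / 55% | 0.2 | 15.5% | 24.4% |
| 55% / 55% | 0.4 | 25.9% | 33.7% |
| 70% / 40% | 0.1 | 11.7% | 18.4% |
| 70% / 40% | 0.2 | 18.3% | 21.8% |
| 70% / 40% | 0.4 | 31.6% | 28.6% |

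For example, the last Betafoam entry is 0.4 × [1 − 0.95 × 0.30] + 0.6 × 0.05 = 0.286 + 0.030 = 0.316. With equal clearance the assumed advantage shrinks to 8.9 or 7.8 points and survives. Among these rows it reverses only when the highest f is combined with the assumed gap in clearance.

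**The case against.** **Few subjects may be affected.** Exclusion criterion 6 removes "Signs of a current underlying systemic infection (sepsis/bacterial infection/tuberculosis) or cellulitis or osteomyelitis", and the precautions in Protocol Sections 13.1 and 13.2 have pus dealt with before either product goes on an infected wound. Purulent and serous can also both be ticked at baseline, and later serous drainage is then not additional. This stands as a limit on size. It does not remove the problem: criterion 6 does not name an infection confined to the ulcer, and the endpoint definition itself provides for subjects infected at baseline.

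**Additional could mean on top of signs that persist.** On that reading, replacing one sign with another would not count. The text does not say so, and its comparison with the signs confirmed at baseline favours the literal reading. If both readings are defensible, an open-label trial should settle the choice before analysis.

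**A reader might infer that the rule works against Betafoam and could erase or reverse a real advantage.** The documents do not support this. Section 5.1 expects a lower risk of infection; it does not say that Betafoam clears existing pus faster. The reversal in the table needs a clearance gap and a prevalence that appear nowhere in the plan.

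**The endpoint is minor.** It is the fourth of the other endpoints in an exploratory pilot of 20 subjects, and no endpoint of main interest is touched. Tables 0705 and 0706 show purulent and serous counts by visit and arm, which partly exposes the pattern but not individual transitions. This limits the importance of the point. The miscoding itself remains.

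**Conclusion.** The point holds as a defect in the derivation rule. Read literally, Protocol Sections 15.3 and 16.1 and SAP Section 7.1 count clearing from purulent to serous-only drainage as a new infection, provided that serous was not ticked at baseline, and do not count persisting pus. No text exempts serous exudate, requires baseline signs to persist, requires a net worsening or calls for culture confirmation.

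The size is 10 percentage points of an arm's incidence per affected subject, assuming 10 analysed subjects per arm and no other event in that subject. The number of affected subjects is not known, and neither is any difference between arms. A bias in a particular direction, or a reversed comparison, is therefore not shown. The correction should be made before analysis, since it is cheap and the rule gives a wrong classification, but it concerns a descriptive secondary result.

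**What to change.** In Protocol Sections 15.3 and 16.1 and in SAP Section 7.1, other endpoints, item 4, add: for subjects infected at baseline, a newly ticked serous exudate that replaces purulent exudate present at baseline, with no other new CSSC sign, is not an additional symptom. Derive Table 0707, and the Fisher test named in SAP Section 8 for this endpoint, on that basis. New purulent, sanguinous and all other new signs continue to count.

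A wider rule under which only new pus counts among the exudate items would also discard new sanguinous exudate, and is not needed here.

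The cost is one sentence and one derivation rule on items already recorded. The downside is that a baseline-infected subject whose only new sign is serous exudate replacing pus is no longer counted; that exudate still appears by visit in Tables 0705 and 0706. The sentence leaves two features as they are: one new sign of another kind is still enough for subjects infected at baseline, and serous exudate still counts where the baseline infection was defined by other signs without pus.

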15.4 Analysis of safety endpoints

(1) Adverse events

List all adverse events that occurred by group. Record the frequency of adverse events related or unrelated with the investigational device by group. For the number of adverse events and the percentage of subjects who had at least 1 adverse event, present the 95% confidence interval in each

treatment group. Analyze adverse events separately for local adverse events at the target pressure ulcer and other adverse events.

(2) Laboratory test findings

For continuous data, present descriptive statistics (mean, standard deviation, median, minimum, maximum) by group and time point. In addition, tabulate the proportion of normal/abnormal results by time point in each group.

(3) Vital signs

For continuous variables, present descriptive statistics (mean, standard deviation, median, minimum, maximum) for the baseline and end-of-study test findings by group and visit time point.

16. Efficacy assessment methods and criteria, and interpretation methods

16.1 Endpoints

(1) Endpoints of main interest

- ① Number of patients with complete healing# of ulcer within 12 weeks
- ② Time to complete healing# of ulcer within 12 weeks

(# The definition of complete healing: Epithelial tissue covering 100% of the study ulcer, no abrasion or ulceration, intact dermis and epidermis)

- ③ Pressure ulcer size reduction rate based on a scale at each time point

(2) Other endpoints

- ① PUSH reduction rate at each time point compared to the baseline level
- ② Dressing change frequency during the entire study period
- ③ Number of subjects with early completion due to complete healing# during the study
- ④ Incidence of new infections** at the pressure ulcer until Week 12 based on the CSSC

(** Infection: Presence of 'Purulent exudates' or 2 or more symptoms of the CSSC. However, for subjects with an infection at baseline, it is defined as development of an additional symptom other than those confirmed at baseline or recurrence of baseline-identified symptoms after being completely healed.)

16.2 Assessment criteria and methods

This study is a pilot study with no comparator, so that no formal statistical test will be conducted.

17. Safety assessment methods and criteria, and interpretation methods, including adverse events

17.1 Assessment method

An adverse event (AE) is any unintended sign (including abnormal laboratory finding), symptom, or disease occurring in a subject during the study, and does not necessarily have a causal relationship with the relevant investigational device.

An adverse device effect(ADE) is any untoward and unintended reaction caused by an investigational

device for which a causal relationship with the investigational device cannot be ruled out.

It is the responsibility of the principal investigator and sub-investigators to record all adverse events occurring during the study. Adverse events are to be recorded according to the MedDRA (Medical Dictionary for Regulatory Activities) and in case it is not possible, terms on signs and symptoms observed by the principal investigator or sub-investigators or spontaneously reported by a subject are to be recorded using medical terms.

In the Case Report Form, signs and symptoms of the adverse event, duration (onset and resolution dates), severity, causal relationship with the study device, action taken for the adverse event, and outcome should be recorded without omission.

The followings will be evaluated for safety assessment.

1) Adverse event

At every visit, review both local adverse events at the target pressure ulcer and other adverse events.

(Local adverse events at the target pressure ulcer: Erythema, edema, itching, flare, rash, others)

2) Vital signs

Vital signs are analyzed by measuring at every visit until study completion. Measured vital signs are blood pressure (in sitting), pulse, and body temperature. In addition, body weight is measured at screening, Week 4, and at the End-of-Study visit.

3) Laboratory tests and physical examination

Laboratory tests are conducted at screening and study completion. For physical examination, normal/abnormal status of findings at screening is confirmed, and it is assessed whether the subject is eligible for study participation.

17.2 Assessment criteria

(1) Severity of the adverse event

Severity (intensity) of an adverse event is assessed using the following criteria.

- ① Mild: While signs or symptoms can be perceived, they can be easily tolerated.
- ② Moderate: May interfere with daily activities.

- ③ Severe: It is not possible to engage in daily activities.

(2) Causal relationship with the investigational device

In case of an adverse event, the relationship with the investigational device is classified by a treating physician as follows, and the sub-investigator's opinion is specified.

● **Definitely related**

- There is the evidence that the study device was used, and there is a reasonable temporal relationship with the adverse event occurrence.
- The adverse event is most plausibly explained by application of the study device than any other reasons.
- The adverse event disappears upon discontinuation of the study device application.
- Outcome of re-application (only when possible) of the study device is positive.
- The event shows a consistent profile with already known information for the study device or medical devices in the same class.

● **Probably related**

- There is the evidence that the study device was used, and there is a reasonable temporal relationship with the adverse event occurrence.
- The event is most plausibly explained by application of the study device than any other reasons.
- The event disappears upon discontinuation of the study device application.

● **Possibly related**

- There is the evidence that the study device was used, and there is a reasonable temporal relationship with the adverse event occurrence.
- The event is determined to be equally attributable to application of the study device as to other possible causes.
- The event disappears upon discontinuation of the study device application.

● **Possibly not related**

- There is the evidence that the study device was applied.
- There is more likely cause of the event.
- Outcome of discontinuation of the study device application is negative or ambiguous.
- Outcome of re-application of the study device is negative or ambiguous.

- **Definitely not related**
 - The subject has not applied the study device.
 - There is no reasonable temporal relationship between the study device application and the adverse event occurrence.
 - There is other clear cause of the event.

- **Unknown**
 - There is insufficient evidence to determine the relationship.
 - Source data has poor quality or data are not consistent.

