14.1 Discontinuation and withdrawal criteria

In case of meeting the following criteria for study device discontinuation, application of the study device and the study should be discontinued, and the reason for discontinuation and findings should be recorded in the Case Report Form.

- Criteria for discontinuation of the study device application

- 1) Acute reactions (allergy, hypersensitivity reactions, etc.) to the study device

- 2) It is determined that continuation of the study is difficult due to an accidental intercurrent condition.
- 3) It is determined that continuation of the study is impossible due to worsening of the pressure ulcer (Stage 4 or higher).
- 4) Debridement was performed during the study, after the study device application.
- 5) Pregnant during the study period
- 6) It is otherwise determined by the investigator that continued application of the study device is not appropriate due to reasons such as serious malnutrition, etc.
- 7) It is determined by the investigator that study participation is not appropriate due to a “serious adverse event”.

“Serious adverse event” is an event, irrespective of a causal relationship with the study device, that is as follows:

- ① Results in death or is life-threatening
- ② Requires inpatient hospitalization or prolongation of existing hospitalization
- ③ Results in persistent or significant disability or dysfunction
- ④ Results in congenital anomaly or birth defect
- ⑤ Other medically important events as identified by the Investigator

In case of discontinuation due to worsening of a pressure ulcer, the treating physician will ensure safety of the patient with appropriate tests and treatment, equivalent to the case of an adverse event.

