17.3 Adverse event reporting method

The principal investigator or sub-investigators will inform the subject or guardian of all possible adverse events after the investigational device application, and instruct them to report all events occurring after the study device application.

For all local, systemic, and clinical pathological findings after using the investigational device, the type, onset time, intensity, treatment, drug, course, causal relationship with the investigational device will be recorded and retained in the subject's Case Report Form, according to the Korea Good Clinical Practice for a Medical Device (enforcement date 2016.01.29).

A serious adverse event(SAE) is an adverse event occurring after the investigational device application that corresponds to any of the followings:

- ① Results in death or is life-threatening
- ② Requires inpatient hospitalization or prolongation of existing hospitalization
- ③ Results in persistent or significant disability or dysfunction
- ④ Results in congenital anomaly or birth defect
- ⑤ Other medically important events as identified by the Investigator

In the event that is not included in the above-listed conditions but is thought to likely have a serious influence on the subject's well-being and health in medical aspects, it will be determined whether the event should be considered a serious adverse event at the medical discretion of the investigator and relevant experts, and an appropriate measure will be taken accordingly.

The principal investigator should also review Serious Adverse Event Reports from other sites as notified by the sponsor, and report them according to the SOP of the site IRB.

Unexpected adverse device effect is an event that has a different profile of the adverse device effect or extent of the risk in light of available information on the medical device, such as the Investigator's Brochure or package insert.

All serious and unexpected adverse device effects should be reported within the timeline classified as follows.

<Reporting timeline to the Ministry of Food and Drug Safety>

- (1) In case of a subject's death or seriously life-threatening event during the study, within 7 days after being informed of the event. However, in this case, further information should be additionally reported within 8 days after the initial reporting date.
- (2) For all other serious and unexpected adverse device effects, within 15 days after the sponsor is informed or learned of the event.

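### Section 17.2 makes disappearance on stopping the device a criterion of every 'related' category, which conflicts with the ADE definition in 17.1, and the SAP has no rule for which categories count as ADE

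*Protocol*

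**What the plan says.** Protocol section 17.2 grades causality in six categories, each with a bullet list.

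- Definitely related includes "The adverse event disappears upon discontinuation of the study device application". The next bullet concerns re-application and is qualified: "Outcome of re-application (only when possible) of the study device is positive".
- Probably related and Possibly related each include "The event disappears upon discontinuation of the study device application", with no qualifier.
- Possibly not related includes a more likely other cause, "Outcome of discontinuation of the study device application is negative or ambiguous", and a negative or ambiguous re-application outcome.
- Unknown covers insufficient evidence or poor source data.

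Section 17.1 defines an ADE differently, as an untoward reaction caused by a "device for which a causal relationship with the investigational device cannot be ruled out".

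Section 14.1 (repeated in SAP section 5) says that when a listed criterion is met, "application of the study device and the study should be discontinued". No temporary interruption is described.

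Three outputs depend on relatedness:

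- Section 15.4 and SAP section 8 ask for a two-way count: "Record the frequency of adverse events related or unrelated with the investigational device by group".
- SAP Table 1101 summarises ADE and SADE by arm, and Tables 1103 and 1105 list them by system organ class and preferred term.
- Section 17.3 ties regulatory reporting to ADE status: "All serious and unexpected adverse device effects should be reported within the timeline classified as follows".

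**The concern.** A causality scale needs a place for an event that may well be due to the device but for which stopping the device told us nothing, or for which stopping did not help. In section 17.2 even the weakest related category expects a positive dechallenge. The authors could qualify a criterion, as they did for re-application under Definitely related, but they did not qualify this one.

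The events affected are realistic. Erythema and itching are among the local events named in section 12.2.7, and a mild one may settle while dressing changes go on. Persistent and fatal events are rarer but matter more.

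At stake are the device-attributed safety tables and the set of events that section 17.3 puts on the 7-day and 15-day reporting timelines. Ratings are made open-label, so cases the rules leave unassigned can be sorted differently in the two arms.

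**Working it through.** The documents state no ADE rate, so there is no plan figure to reproduce. The check is textual, with an illustration of scale.

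**Step 1. Which category is reachable?** Take each list in 17.2 as written, with its bullets required together, and cross the course of the event with its attribution. Definitely not related is set aside because its bullets read as alternatives.

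| Course of event | Device most plausible | Equally plausible | Other cause more likely |
|---|---|---|---|
| Device stopped, event clears | Probably (Definitely if its other bullets hold) | Possibly | none: Unknown |
| Device stopped, event persists | none: Unknown | none: Unknown | Possibly not* |
| Fatal | none: Unknown | none: Unknown | Possibly not* |
| Clears while the dressing continues | none: Unknown | none: Unknown | Possibly not* |

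*Only if an outcome that was never obtained (re-application, and in the last row dechallenge) may be read as ambiguous.

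In the lower three rows, six cells with the device at least equally plausible have no related category. They also fail Possibly not related, because no other cause is more likely.

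**Step 2. Compare with 17.1.** In those six cells causality has not been ruled out, so the events meet the 17.1 definition. Section 17.2 gives them a label without the word related. The two sections therefore disagree on the same event.

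**Step 3. Look for a rule that settles it.** Section 15.4 and SAP section 8 ask for related versus unrelated; SAP Tables 1101, 1103 and 1105 use ADE and SADE. The SAP expands these abbreviations but does not define them. No text maps the six categories to either split, and Unknown is unassigned.

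**Step 4. Size.** With 10 subjects per arm, one reclassified subject is 1/10 = 10 percentage points. Exact (Clopper-Pearson) 95% intervals for n = 10 are:

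- 0/10: 0 to 30.8% (upper limit 1 − 0.025^(1/10))
- 1/10: 0.3 to 44.5%
- 2/10: 2.5 to 55.6%
- 3/10: 6.7 to 65.2%

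Now let p be the true ADE risk per subject and q the share of those subjects who can show positive dechallenge. Both are assumptions. If ADE means the three related categories, the expected count per arm is 10pq, and the chance of counting at least one is 1 − (1 − pq)^10.

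| p | expected, q = 1 | q = 0.5 | q = 0.25 |
|---|---|---|---|
| 10% | 1.0 | 0.5 | 0.25 |
| 20% | 2.0 | 1.0 | 0.5 |
| 30% | 3.0 | 1.5 | 0.75 |

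At p = 20% the chance of counting at least one is 1 − 0.8^10 = 89% (q = 1), 1 − 0.9^10 = 65% (q = 0.5) and 1 − 0.95^10 = 40% (q = 0.25). If ADE follows 17.1, the count does not depend on q and the loss is zero.

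**The case against.** **The bullets may not all be required.** Section 17.2 never says they are. The Definitely not related list works only as alternatives, since no treated subject could meet its first bullet. This stands, and it means that bullet does no harm and need not be deleted. It does not repair the other lists, where nothing tells the rater that dechallenge may be waived.

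**Subjects who stay on treatment are not shut out.** A reader might infer that, because a stopping criterion ends participation, no event in a subject who completes treatment can be rated related. The documents do not support this. Device use ends for everyone at early completion or 85d, and section 17.4 follows adverse events until they resolve or stabilise. An event present at that point that then clears meets the criterion. Section 14.1 does not forbid interruption either, and 17.2 itself contemplates re-application. What remains is the lower three rows of the first table.

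**Under-counting is not certain.** A reader might infer that ADEs will be under-counted. That requires ADE to mean the three related categories, which neither document says. Under 17.1 the events would be counted. The gap is that the SAP leaves the choice open.

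**The events are not lost.** All adverse events are listed by arm, Table 1101 gives local and other events whatever their causality, and Tables 1109 and 1115 break them down by relationship. Serious events go to the sponsor within 24 hours of the investigator's knowledge, regardless of causality. This limits the harm, but it does not settle what enters the ADE and SADE rows or which events are treated as ADEs for the regulator.

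**Conclusion.** The inconsistency is real and narrow. As written, 17.2 gives no related rating to events that persist after stopping, are fatal, or resolve during continued use, even with the device an equally or more plausible cause, while 17.1 treats such events as ADEs. No rule connects the two.

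The effect on results is conditional. If ADE and SADE are derived from the three related categories, the counts err downward by 10 percentage points per affected subject in an arm of 10. If they are derived from 17.1, there is no loss. The conclusion rests on reading each related list as a set of joint requirements, which is the natural reading but is not stated. The values of p and q are illustrative. In a 20-subject exploratory pilot this does not threaten the study, but it should be settled before the ADE tables are produced, because ratings are open-label and regulatory reporting uses the same term.

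**What to change.** In Protocol section 17.2, apply the dechallenge bullet only where the device was actually stopped and the outcome can be assessed. Apply the re-application bullet under Possibly not related only where the device was re-applied and the outcome can be assessed. State that Possibly related may stand when dechallenge information is lacking or negative.

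In the SAP, define ADE and SADE for Tables 1101, 1103 and 1105, and the related/unrelated split in section 8, in line with Protocol 17.1. State explicitly that Unknown counts as an ADE, and how Possibly not related is treated. The latter is a policy choice, because that category has a more likely other cause, but it must be written down. Use the same definition for reporting under 17.3. Keep the six-level split in Tables 1109 and 1115 so that readers can see what each category contributes.

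The cost is a wording change in one protocol section and one derivation rule in the SAP, with no new data. Reported ADE counts may be somewhat higher. No change to the device-stopping rules is proposed.
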